13 ETHICS AND REGULATORY COMPLIANCE

13.1 Conduct of the Clinical Study

Conduct of the clinical study will follow QAPs from Acutus Medical, as well as the Code of Federal Regulations (CFRs), Declaration of Helsinki, GCPs, EN ISO 14155:2011, and other regional and local laws. Each Investigator must sign and date the IA prior to the start of this clinical study. With the signature, the Investigator agrees to perform all clinical study procedures according to the governing local and national regulations and the CIP/protocol.

13.2 Institutional Review Board/Ethics Committee Approval

A properly constituted, valid IRB/EC must review and approve the CIP/protocol, ICF, and related patient information and recruitment materials prior to initiation of the clinical study. It is the responsibility of the Investigator and/or Sponsor to obtain protocol approval from the institution's IRB/EC, and to keep the IRB/EC informed of any SAEs or SADEs and amendments to the protocol. Additional requirements imposed by the IRB/EC or other regulatory authority shall be followed as appropriate. All correspondence with the IRB/EC should be filed by the Investigator and copies sent to Acutus Medical (or designee).

13.3 Competent Authority Approval

For European clinical study sites, it is the responsibility of the Sponsor to obtain protocol approval from the country's Competent Authority, and to keep the CA informed of any SAEs or SADEs and amendments to the protocol. Additional requirements imposed by the CA or other regulatory authority shall be followed as appropriate. All correspondence with the CA should be filed in the TMF.

13.4 Clinical Study Informed Consent Approval

In accordance with the principles of Informed Consent, 21 CFR Part 50, the Declaration of Helsinki, GCP, and EN ISO 14155:2011, ICF will be obtained and documented in writing before a patient is enrolled in the clinical study.

It is the responsibility of the Investigator to ensure that a written ICF is obtained from the subject (or legally acceptable representative) before any activity or procedure is undertaken that is not part of routine care. Information obtained during the conduct of the clinical study that may impact the patient ICF may require revisions to the ICF. If so, revisions and approvals of such changes by the appropriate regulatory authority is required. Documentation of the current versions of the informed consent will be documented in the clinical study TMF.

13.5 Identification and Confidentiality

Subject identification and confidentiality will be ensured in accordance with all applicable regulatory and IRB/EC governance. This includes, but is not limited to, the following:

- Subjects will be identified on all eCRFs and source documents by a unique anonymized identification reference number.
- eCRFs are confidential documents and will only be made available to Acutus Medical (and appropriate designees), the Investigator, the biostatistician, and, if requested, to advisory committees and regulatory authorities (including the FDA).
- Data will be stored in accordance with regulations for handling of electronic data.

The site will maintain (anonymous to Acutus Medical) a list identifying all subjects entered into the clinical study. The list will be maintained as part of the Investigator Site File (ISF) file and monitored for completeness.

13.6 Site Qualification Visits

A Site Qualification Visits (SQV) will follow Acutus Medical QAPs.

13.7 Site Initiation Visits

All clinical study personnel will be required to participate in a Site Initiation Visit (SIV) that follows Acutus Medical's QAP. Portions of the SIV training may be completed via a web access meeting. Components of this initiation visit may include:

- Introduction of the clinical study design including the protocol-specific treatment and follow-up phase
- ICF process

- Product training to all end-users
- eCRF completion training
- Safety reporting instructions
- Training on the regulations governing human research
- Procedure training on the use of the device

13.8 Insurance

Acutus Medical shall maintain insurance coverage for this clinical study. Pertinent information regarding the coverage shall be made available to the site upon request.

13.9 Site Audit Plan

Participation as an Investigator in this clinical study implies acceptance of potential inspection by government regulatory authorities and applicable compliance and quality assurance offices. The Investigator and/or designee must be available to respond to reasonable requests and queries made by authorized regulatory representatives during the audit process. The Investigator must provide Acutus Medical with copies of all correspondence that may affect the review of the current clinical study or their qualifications as an Investigator in this and future clinical studies conducted by Acutus Medical.

13.9.1 Site Data Audits by Acutus Medical

In accordance with local and national regulations and Acutus Medical's QAPs, an internal audit may be requested to access all clinical study records, including source documents, for inspection and duplication. The Investigator will ensure the capability for inspections of applicable clinical study-related functions.

A site data quality assurance audit may be conducted during the clinical study.

13.9.2 External Audits

Requests by regulatory agencies to inspect the clinical study sites may be made as well. The Investigator and/or designee is required to report to Acutus Medical as soon as possible after receiving a request from a regulatory authority to perform an audit. The clinical Investigator agrees to allow inspectors from regulatory agencies to review records and to assist the inspectors in their duties, if requested.

13.10 Public Domain Access to the Clinical Study

A description of this clinical study will be available on http//www.Clinicaltrials.gov. Information regarding the public access will be presented in the ICF.

13.11 Required Reports

Acutus Medical will remain in compliance with all required and pre-specified reports during the enrollment and follow-up of the clinical study. IRB/EC/CA requirements for reports will be provided as requested.

14 GENERAL CONSIDERATIONS

14.1 Discontinuation of the Clinical Study

The Sponsor reserves the right to discontinue the clinical study at any stage, with suitable written notice to the Investigator and the appropriate government regulatory agencies. Similarly, Investigators may withdraw from the study, subject to providing written notification to the Sponsor within thirty (30) days of their intent to withdraw. However, the Sponsor and Investigators will be bound by their obligation to complete the follow-up of subjects already enrolled into the clinical study.

Acutus Medical, as Sponsor, may terminate Investigator and site participation in the clinical study if there is evidence of an Investigator's failure to maintain adequate clinical standards or evidence of an Investigator's or staff's failure to comply with the CIP/protocol/or IA.

Notification of suspension or termination will occur no later than five (5) business days after Acutus Medical makes the determination. In the event of clinical study suspension or termination, Acutus Medical or designee will send a report outlining the circumstances to the reviewing IRB/EC/CA, the appropriate regulatory agencies, and to all participating Investigators. Any suspension or termination may not be re-initiated without prior approval of the IRB/EC/CA and Acutus Medical.

14.2 Use of Information and Publications

All information concerning Acutus Medical operations, patent applications, manufacturing processes, and basic scientific data supplied by Acutus Medical to the Investigator and not previously published, are considered confidential and remain the sole property of Acutus Medical. This includes all clinical study materials, worksheets, and eCRFs.

The information developed in this clinical study may be used by Acutus Medical as support for a regulatory filing and in connection with the continued development of the AcQBlate Force Sensing System. Any publication or other public presentation of the data resulting from this clinical study will require prior review and written approval of Acutus Medical.

At the conclusion of the clinical study, it is expected that Acutus Medical and the Investigators will promptly prepare and submit a manuscript for publication in a reputable scientific journal.

Further analyses, beyond those presented in the initial publication may be proposed to Acutus Medical. For purposes of timely abstract presentation and publication, such secondary

AcQForce Flutter

publications may be delegated to the appropriate principal authors; however, final analyses and manuscript review for data will require the prior written approval of Acutus Medical.

None of the results, in whole or part, of the clinical study carried out under this CIP/protocol, nor any of the information provided by Acutus Medical for the purposes of performing the clinical study, will be published or passed on to any third party without the consent of Acutus Medical. Any Investigator involved with this clinical study is obligated to provide Acutus Medical with complete test results and all data derived from the clinical study.

15 References

- 2. Wellens HJJ. Contemporary management of atrial flutter. *Circulation*. 2002;106(6):649-652. doi:10.1161/01.CIR.0000027683.00417.9A

3	Clini	cal Study Objective
4	Stud	y Design6
5	Sam	ple Size DeterminationError! Bookmark not defined.
	5.1	Assumptions for Statistical AnalysisError! Bookmark not defined.
	5.2	Study Sample Size RationaleError! Bookmark not defined.
6	Stati	stical Analyses6
	6.1	General Considerations
	6.1.1	Descriptive Statistics
	6.1.2	Study Day6
	6.1.3	Visit Windows
	6.1.4	Statistical Significance
	6.1.5	Precision7
	6.2	Analysis Populations
	6.3	Handling of Missing Data8
	6.4	Subject Disposition
	6.5	Demographics and Baseline Characteristics9
	6.6	Analysis of Study Endpoints9
	6.6.1	Primary Safety Endpoint9
	6.6.2	Primary Efficacy Endpoint
	6.6.3	Other Safety Analyses
	6.6.4	Observational Effectiveness Endpoint12
	6.7	Poolability Analyses
	6.8	Subgroup Analyses
	6.9	Interim Analyses
	6.10	Protocol Deviations
7	Char	ges from Planned Analyses
8	Subj	ect Listings

Statistical Analysis Plan Page			4 of 14
Sponsor	Study		Version
ACUTUS Medical	S AcQBlate Force Sensing Ablation System		2.0

1 Introduction

This statistical analysis plan (SAP) describes the planned statistical methods for the reporting and analysis of data collected under the Clinical Investigation Protocol AcQBlate Force Sensing Ablation System US IDE for Atrial Flutter (AcQForce Flutter) (CLP-21) and Clinical Investigation Protocol AcQBlate Force Sensing Ablation System EU Study for Atrial Flutter (AcQForce Flutter-EU) (CLP-21-EU). Data from these studies will be used to support a pre-market approval (PMA) application.

This SAP should be read in conjunction with the study clinical investigation plan (CIP) and case report forms (CRFs). This version of the SAP has been developed with respect to the Clinical Investigation Protocol AcQBlate Force Sensing Ablation System US IDE for Atrial Flutter (AcQForce Flutter) Rev 12 19Oct2021 and Clinical Investigation Protocol AcQBlate Force Sensing Ablation System EU Study for Atrial Flutter (AcQForce Flutter-EU) Rev 02 21May2021. Any revisions to the protocols or CRFs that impact the planned analyses may require updates to the SAP.

Document Number, Version	Document Title
CLP-21, Rev 12	Clinical Investigation Plan for AcQBlate Force Sensing Ablation
	System US IDE for Atrial Flutter (AcQForce Flutter)
CLP-21-EU, Rev 03	Clinical Investigation Plan for AcQBlate Force Sensing Ablation
	System EU Study for Atrial Flutter (AcQForce Flutter-EU)
CLP-21-DE Rev 01	Clinical Investigation Plan for AcQBlate Force Sensing Ablation
	System DE Study for Atrial Flutter (AcQForce Flutter-DE)
QAP 3.8	Quality Assurance Procedure for Clinical Studies

Applicable Documents:

2 Abbreviations

Abbreviation/Term	Definition
AAD	Antiarrhythmic drug
AE	Adverse Event
ASD	Atrial Septal Defect

Statistical Analysis Plan Page			5 of 14
Sponsor	Study		Version
ACUTUS Medical	AcQBlate Force Sensing Ablation System US IDE/EU Study for Atrial Flutter (AcQForce Flutter & AcQForce Flutter-EU)		2.0

BDB	Bidirectional Block
CIP	Clinical Investigational Plan
COPD	Chronic Obstructive Pulmonary Disease
CRF	Case Report Form
СТІ	Cavotricuspid Isthmus
DCCV	Direct Current Cardioversion
ECG	Electrocardiogram
eCRF	Electronic Case Report Form
ICD	Implantable Cardioverter Defibrillator
IDE	Investigational Device Exemption
ITT	Intention-to-Treat
mITT	Modified Intention-to-Treat
OUS	Outside of United States
PFO	Patent Foramen Ovale
PMA	Premarket Approval
РРТ	Pre-procedure Testing
RF	Radiofrequency
SADE	Serious Adverse Device Effect
SAE	Serious Adverse Event
SAP	Statistical Analysis Plan
SAS	Statistical Analysis System
SSED	Safety and Effectiveness Data
TIA	Transient Ischemic Attack
US	United States

3 Clinical Study Objective

The objective is to demonstrate that the AcQBlate Force Sensing System is safe and effective when used to ablate the cavotricuspid isthmus (CTI) for the treatment of typical atrial flutter when compared to a literature-based control.

Data will be used to support a PMA application.

St	6 of 14		
Sponsor	Study		Version
ACUTUS Medical	AcQBlate Force Sensing Ablation System US IDE/EU Study for Atrial Flutter (AcQForce Flutter & AcQForce Flutter-EU)		2.0

4 Study Design

The AcQForce Flutter and AcQForce Flutter-EU clinical studies are prospective, multi-center, non-randomized, global clinical studies designed to confirm the safety and efficacy of the AcQBlate Force Sensing System. All subjects with typical atrial flutter will undergo percutaneous catheter ablation of the cavotricuspid isthmus using the AcQBlate Force Sensing System with the endpoint of achieving bidirectional block (BDB). Treated subjects will have data collected at screening, procedure, pre-hospital discharge, and 7-and 30-days post procedure. The subject population will consist of men and women 18 years of age or older, presenting for a *de novo* percutaneous cardiac ablation of the cavotricuspid isthmus for typical atrial flutter. De

5 Statistical Analyses

5.1 General Considerations

Except where otherwise specified, the following general principles apply to the planned statistical analyses. All statistical analysis will be conducted using SAS software version 9.3 or later or other widely accepted statistical or graphical software as required.

5.1.1 Descriptive Statistics

Continuous variables will be summarized as means, standard deviations, medians, and ranges. Categorical variables will be summarized as frequencies and percentages.

Confidence intervals may be presented, where appropriate, using the t-distribution for continuous data and Clopper-Pearson Exact method for categorical variables.

5.1.2 Study Day

Study day 0 is the date of the index procedure. Day in study will be calculated relative to the index procedure as follows:

Study Day = Assessment Date – Index Procedure Date

For each subject, duration in study will be based on last study contact date which is the latest date of all follow-up visits, assessments, adverse event onset or resolution, and study exit including date of death.

Statistical Analysis Plan Page			7 of 14
Sponsor	Study		Version
ACUTUS Medical	AcQBlate Force Sensing Ablation System US IDE/EU Study for Atrial Flutter (AcQForce Flutter & AcQForce Flutter-EU)		2.0

Duration variables will be calculated as follows:

Duration Days = End Date – Start Date

5.1.3 Visit Windows

Unless otherwise specified, visit based assessments will be analyzed for each analysis time point according to the nominal visit entered in the Case Report Form (CRF) regardless of if it is out of window.

5.1.4 Statistical Significance

Confidence intervals and statistical tests will be performed at a two-sided 5% significance level unless specified otherwise. P-values will be rounded to four decimal places. If a p-value is less than 0.001 it will be reported as "<0.001".

5.1.5 Precision

Unless otherwise specified, the following conventions will apply for data display. In general, percentages will be displayed to 1 decimal place. Percentages <0.05% will be reported to 2 decimal places.

5.2 Analysis Populations

The following analysis populations are defined for analysis:

- 1. The **Enrolled Analysis Set** will consist of subjects who have signed an informed consent form, are deemed study eligible by meeting all of the inclusion and none of the exclusion criteria up to the point of the procedure.
- 2. The **Pre-procedure Testing (PPT) Failure Set** will consist of enrolled subjects who have presented for the procedure in any rhythm other than sinus rhythm or typical atrial flutter and have not undergone venous access. These subjects will be treated per the recommendations of the study physician and exited from the study. No use of the investigational device is allowed. A Study Exit electronic case report form (eCRF) will be completed.
- 3. The Intention-to-Treat (ITT) Failure Analysis Set will consist of enrolled subjects who have the venous access portion of the ablation procedure initiated, regardless of whether the AcQBlate FORCE Catheter has been inserted, and up to the point of completion of the right-atrial access but prior to any RF application with the

S	tatistical Analysis Plan	Page	8 of 14
Sponsor	Study		Version
ACUTUS Medical	AcQBlate Force Sensing Ablation System US IDE/EU Study for Atrial Flutter (AcQForce Flutter & AcQForce Flutter-EU)		2.0

investigational device. The ITT Failure subjects will be followed for safety reasons through the 7-day follow-up visit. All ITT Failure subjects will be excluded from any efficacy data analysis. In addition to the Discharge eCRF and the 7-day Follow-up eCRF, a Study Exit eCRF will also be completed. The ITT Failure population may include:

- At the time of the procedure, if the subject does not demonstrate conduction through cavotricuspid isthmus, the subject will be exited from the study and followed for safety through the 7-day follow-up visit.
- At the time of procedure, if atrial fibrillation is initiated during the process of inducing typical AFL, a direct current cardioversion (DCCV) may be performed to attempt conversion to sinus rhythm so that the CTI conduction portion of the study may proceed. If during confirmation of the CTI conduction, the investigator determines that further ablation beyond the CTI is warranted the subject will be exited from the study and followed for safety through the 7-day follow-up visit.
- 4. The Modified Intention-to-Treat (mITT) Analysis Set will consist of enrolled subjects who initiates the ablation procedure using the AcQBlate Force Sensing System. An initiated ablation procedure is defined as a procedure where the AcQBlate Force Sensing System is used for the ablation procedure irrespective if a non-investigational device was used to complete the ablations. mITT subjects will be followed for all study outcome measures for the full duration of the clinical study and will comprise the data set for the Primary Efficacy Endpoints.

5.3 Handling of Missing Data

All attempts will be made to limit the amount of missing data. Unless otherwise specified, no attempt will be made to impute missing data. If a data point is missing, that data point will not contribute to that portion of the analysis. The number of evaluable observations will be reported in analysis so that extent of missing data can be assessed. Sensitivity analyses will be performed for the primary safety and efficacy endpoints as detailed in Section 6.6.

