7.6.4 Confirmation of Bidirectional Block

Initial bidirectional block (BDB) confirmation should meet the study endpoint definition of:

• Demonstration of bidirectional electrophysiological conduction block through the cavotricuspid isthmus (CTI) using both coronary sinus ostium (CS) and annular low right atrial pacing maneuvers.

This acute endpoint should be re-confirmed at least 20-minutes following the last RF ablation with the investigational device. If recovery of isthmus conduction occurs, additional ablations should be performed at the site of the reconnection, and the confirmation/reconfirmation steps must be repeated. A reset of the 20-minute wait time for reconfirmation is required. A second investigative catheter or alternate catheter curve may be used prior to designation as ablation failure. Maximum RF time before considering a non-investigational catheter is at the discretion of the Investigator but shall not exceed 60 minutes of RF time. If the Investigator is unable to achieve bidirectional block with the investigational catheter(s), it is recommended, at the Investigator's discretion, to use a commercially available ablation catheter approved for typical atrial flutter to complete the procedure.

7.7 **Post Ablation Recovery**

At the conclusion of the procedure, the subject should be recovered following the Institution's standard practice. Sheath removal may be completed when acceptable hemostasis can be achieved. The use of protamine to reverse anticoagulation is at the discretion of the Investigator. Protamine use will be recorded on the Procedure eCRF.

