7.8 Procedure Data Collection

Collection of data generated as a result of the procedure should include:

- Print out of 12-lead ECG at procedure start
- Print out of intracardiac AFL
- Print out of entrainment pacing results pre-ablation for the CTI
- Print out of attempts to prove conduction through the CTI
- Print out of 12-lead ECG at end of procedure
- Demonstration of initial BDB
- Demonstration of BDB 20 minutes following initial determination
- Total procedure time (from first venous access to last cardiac catheter removed)
- Total ablation time for CTI ablation
- Total fluoroscopy time for the CTI ablation procedure
- Cumulative irrigation volume for CTI ablation
- Pre-set parameters for RF power and temperature
- Maximal parameters for RF power and temperature for CTI ablation
- Number of RF applications for CTI ablation

- Cross over of any non-investigational catheter (including reason for change out)
- Recording of all IV cardiac medications and anticoagulation infused during the procedure
- Usability characteristic data will be collected.
- Device identification

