8.4 Study Success Criteria

The study success criteria is defined as the rejection of the null (Ho) hypotheses for safety and efficacy as defined in sections 8.2.1 and 8.3.1, respectively.

• Safety Ho: The proportion subjects in the mITT and select ITT subjects (ρ) who are free from device/procedure related SAE through 7-days post ablation procedure is less than or equal to 93.0%.

Ho:
$$\rho \le 93.0\%$$

Efficacy Ho: The proportion of mITT subjects (β) demonstrating bidirectional block (BDB) of the CTI confirmed at 20 minutes following the last right atrial radiofrequency (RF) application using the investigational catheter is less than or equal to 83.7%.

Ho:
$$\beta \le 83.7\%$$

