5.6 Analysis of Study Endpoints

5.6.1 Primary Safety Endpoint

The primary safety endpoint is defined as the proportion of mITT and select ITT Failure subjects (i.e., subjects who had the AcQBlate FORCE Catheter inserted) who are free from a composite list of pre-specified device/procedure related SAEs that occur through 7-days post ablation procedure. Subjects who do not have evidence of a SAE/SADE from the composite list of safety events will be considered a success.

Serious adverse events that meet the definition for Primary Safety Endpoint are pre-defined and include:

- Death
- Cardiac tamponade/perforation
- Myocardial infarction
- Stroke
- Systemic embolism
- Major access site complications
- Major bleeding requiring transfusion
- Complete heart block
- Other SAEs/SADEs adjudicated by an independent review as "probably or definitely related" to the Investigational device.

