5.6.2 Primary Efficacy Endpoint

The primary efficacy endpoint is defined as the proportion of mITT subjects (β) achieving acute procedural success. Acute procedural success is defined as the demonstration of bidirectional cavotricuspid isthmus block confirmed at least 20 minutes following the last radiofrequency (RF) application at the cavotricuspid isthmus with the investigational catheter.

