5.6.2.1 Primary Efficacy Endpoint Analysis

The null and alternate hypotheses for primary efficacy endpoint are as follows:

Ho: The proportion of mITT subjects (β) demonstrating bidirectional cavotricuspid isthmus block confirmed at 20 minutes following the last right atrial radiofrequency (RF) application at the cavotricuspid isthmus with the investigational catheter is less than or equal to 83.7%.

St	atistical Analysis Plan	Page	11 of 14
Sponsor	Study		Version
ACUTUS Medical	AcQBlate Force Sensing Ablation System US IDE/EU Study for Atrial Flutter (AcQForce Flutter & AcQForce Flutter-EU)		2.0

Ho: β ≤ 83.7%

Ha: The proportion of mITT subjects (β) demonstrating bidirectional cavotricuspid isthmus block confirmed at 20 minutes following the last right atrial radiofrequency (RF) application at the cavotricuspid isthmus with the investigational catheter is greater than 83.7%.

Ha: β > 83.7%

The null hypothesis will be rejected if the one-sided 95% Clopper-Pearson Exact lower confidence bound is greater than 83.7%.

A primary efficacy failure will comprise the following:

- The inability to achieve and maintain bidirectional CTI block at least 20 minutes following the last RF application with the investigation device. A second investigative catheter or alternate AcQBlate FORCE catheter curve may be used prior to designation as failure. Maximum RF time before considering a non-investigational catheter is at the discretion of the Investigator but shall not exceed 60 minutes of RF time. OR
- The use of a commercially available non-investigational catheter for any ablation of the CTI.

NOTE: Use of isoproterenol is at the discretion of the Investigator.

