5.6.2.2 Sensitivity Analysis

Sensitivity analyses to assess the effect of missing data on the primary efficacy endpoint will be performed including:

• A tipping point analysis in which missing data are varied from worst case to best case to evaluate subjects with missing primary efficacy data in the mITT analysis set.

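### The SAP does not say how a treated subject with no 20-minute block check is counted, so that subject may drop out of the primary efficacy denominator

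*Combined protocol and SAP*

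**What the plan says.** SAP 5.3 (Handling of Missing Data) plans no imputation unless otherwise specified and adds: "If a data point is missing, that data point will not contribute to that portion of the analysis". It also says that the number of evaluable observations will be reported.

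SAP 5.6.2 defines acute procedural success as "the demonstration of bidirectional cavotricuspid isthmus block confirmed at least 20 minutes following the last radiofrequency (RF) application" at the isthmus with the investigational catheter. SAP 5.6.2.1 lists two kinds of failure. One is "The inability to achieve and maintain bidirectional CTI block at least 20 minutes following the last RF application with the investigation device". The other is use of a commercial catheter for any CTI ablation. A check that was never made or never documented is in neither list.

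SAP 5.6.2.2 plans a tipping-point analysis, from worst case to best case, to "evaluate subjects with missing primary efficacy data in the mITT analysis set". For safety, SAP 5.6.1 does state a default: "Subjects who do not have evidence of a SAE/SADE from the composite list of safety events will be considered a success".

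On timing, protocol 7.6.4 asks for block to be re-confirmed at least 20 minutes after the last investigational RF. Where conduction recovers and more RF is given, it adds: "A reset of the 20-minute wait time for reconfirmation is required". The data list in protocol 7.8 words the item differently: "Demonstration of BDB 20 minutes following initial determination".

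Protocol 8.4 ties the outcome of the study to the two primary tests: "The study success criteria is defined as the rejection of the null (Ho) hypotheses for safety and efficacy".

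**The concern.** The primary efficacy test is pass or fail on an exact lower bound, so the denominator has to be fixed before the data are seen. Under the SAP's general rule, a treated subject whose block was never shown at the required time can be treated as missing and left out, although success requires block to be shown. Compared with counting the subject as a non-success, leaving the subject out can only raise the observed rate and its lower bound. Because the text supports either treatment, the choice of primary result could be argued once the data are known.

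Protocol 7.8 shows one way this could arise. If RF is added after first block without recovery of conduction, a check timed from the initial determination may not fall 20 minutes after the last RF.

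**Working it through.** **Inputs.** Performance goal 83.7%, planned rate 93.7%, one-sided 5% level, 90% power and efficacy sample size 85 (protocol 8.1 and 8.8). Study size 110, maximum 120 mITT (protocol 8.8). Decision rule: one-sided 95% Clopper-Pearson lower bound above 83.7% (SAP 5.6.2.1). The number of unchecked subjects, m, is assumed, because the documents give none.

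**The plan's own figure.** For the one-sample z test, n = [(1.645·√(0.837·0.163) + 1.282·√(0.937·0.063)) / 0.10]² = 84.44, rounded up to 85. The stated figure reproduces.

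**Decision rule.** The lower bound for x successes in n is the 5% quantile of Beta(x, n − x + 1). At n = 110 the smallest passing count is 99 (bound 83.99%). The exact error is P(X ≥ 99 | 110, 0.837) = 4.2% and the power at 93.7% is 95.5%.

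**Same data, two denominators.** For each m, take the smallest count that passes with the unchecked subjects left out, then divide the same count by 110.

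| m | Left out | Bound | Counted as failures | Bound |
|---|---|---|---|---|
| 1 | 98/109 | 83.85%, passes | 98/110 | 82.92%, fails |
| 2 | 97/108 | 83.705%, passes | 97/110 | 81.87%, fails |
| 3 | 97/107 | 84.66%, passes | 97/110 | 81.87%, fails |

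At the maximum of 120, 107/119 passes (84.17%) and 107/120 fails (83.33%).

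**False-pass probability with m left out.** Let c be the smallest passing count at 110 − m (98, 97 and 97 for m = 1, 2 and 3).
- Missingness unrelated to outcome: checked subjects succeed at 83.7%, so the probability is P(X ≥ c | 110 − m, 0.837).
- Every unchecked subject a non-success: the rate over all 110 is 83.7%, so the rate among checked subjects is 0.837 × 110/(110 − m), which is 84.47%, 85.25% and 86.05%.

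| m | Unrelated to outcome | All unchecked are non-successes |
|---|---|---|
| 0 | 4.2% | 4.2% |
| 1 | 4.6% | 7.0% |
| 2 | 5.0% | 11.1% |
| 3 | 2.9% | 10.4% |

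The values fall from m = 2 to m = 3 because the test is discrete: 11 observed failures are allowed at n = 108 but only 10 at n = 107.

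**Pass probability when checked subjects succeed at 93.7%.** Left out: P(X ≥ c | 110 − m, 0.937). Counted as failures: P(X ≥ 99 | 110 − m, 0.937).

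| m | Left out | Counted as failures | Difference (points) |
|---|---|---|---|
| 1 | 95.8% | 91.7% | 4.1 |
| 2 | 96.0% | 85.7% | 10.4 |
| 3 | 92.6% | 76.7% | 15.8 |

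Differences are taken before rounding. Each is the probability that the two readings give opposite verdicts.

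**Away from the threshold.** The planned rate implies about 103 successes in 110 (0.937 × 110 = 103.07), or about 7 failures. The rule allows 11 non-successes. Four unchecked subjects on top of 7 observed failures would still give 99/110, which passes.

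**The case against.** The strongest reply is that the endpoint is a proportion of mITT subjects with block demonstrated, that the mITT set is named as the data set for primary efficacy, and that SAP 5.3 applies only unless otherwise specified. On that reading an undemonstrated block is simply not a success. This is a fair reading, and it means that the SAP permits the drop-out without requiring it. Nor does the tipping-point analysis prove that unchecked subjects leave the primary denominator: SAP 5.6.1.2 plans one for safety too, where a default is stated. But SAP 5.6.2 states no such default, and SAP 5.6.2.2 speaks of missing efficacy data in mITT as something other than failure, so the ambiguity stands.

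It is also true that the evaluable number will be reported and that the worst case of the tipping-point analysis counts these subjects as failures. What remains open is which result is primary.

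The check is made during the procedure, so few subjects should lack it. An abandoned procedure arguably already counts as inability to achieve block. Protocol 7.6.4 does require re-confirmation after the last RF, and the eCRF is not in the documents. The wording in 7.8 may therefore produce mistimed checks more often than missing ones.

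A reader might go further and infer that the plan is wrong to exclude subjects whose device fails before any investigational RF. The documents do not support that. The mITT set is a valid treated-subject population, SAP 5.4 reports exclusions with reasons, and the two examples of ITT Failure subjects given in protocol 6.7 and SAP 5.2 are not device failures. Protocol 8.5 is about missing data and does not call for counting pre-RF device failures.

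**Conclusion.** The concern holds as an ambiguity in the denominator of a primary pass/fail test. As worded, the SAP allows an mITT subject with no documented check at 20 minutes or later after the last investigational RF to be left out. The effect is confined to results near the threshold, where one such subject is enough to reverse the verdict. The false-pass figures for one to three unchecked subjects are a range whose ends depend on why the check is missing. It would be wrong to quote only the upper end as the trial's error rate: when missingness is unrelated to outcome, the error stays within the nominal 5%. All of these figures rest on assumed numbers of unchecked subjects.

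A separate and smaller point also stands. Protocol 8.5 plans sensitivity analyses of both primary endpoints in the mITT and select ITT cohorts. Protocol 6.7 and SAP 5.2 keep ITT Failure subjects out of efficacy, and SAP 5.6.2.2 is limited to mITT. These passages conflict. A supportive analysis that counts device failures before the first RF would be optional, and its absence is not an error in the plan.

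**What to change.** 1. In SAP 5.3 or 5.6.2, state that an mITT subject without documented bidirectional block at 20 minutes or later after the last investigational RF application is a failure in the primary efficacy analysis. Keep the tipping-point analysis as supportive.
2. Reword the item in protocol 7.8 so that the check is timed from the last RF, as in the endpoint, and record the time of the last investigational RF and the time of the check.
3. Reconcile protocol 8.5 with protocol 6.7 and SAP 5.2 and 5.6.2.2 on whether any ITT Failure subjects enter an efficacy sensitivity analysis.

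The drafting cost is one SAP sentence, one reworded data item, two time fields and the reconciliation. The statistical cost is the loss of pass probability shown above: at 93.7% among checked subjects, from 95.8% to 91.7% with one unchecked subject and from 96.0% to 85.7% with two. The documents do not say how the trials in protocol Table 1 handled unchecked subjects, so the stricter rule may not match the source of the performance goal exactly. With no unchecked subjects, power at 110 stays at 95.5%, so the sample size need not change. Sites can limit the loss by making and recording the check in every case.
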